4.5. Subject Discontinuation Criteria

For an individual subject, study completion is defined as completing the Treatment Period and the EOS or EOE Visit with the exception for subjects that after Part D Extension transition to the separate Open-Label Extension Study. These subjects will not perform the EOE Visit, hence they will complete Part D Extension at the Day 91 Visit..

Subjects will be free to discontinue the study at any time for any reason. Subjects may be discontinued from the study by the Investigator, if necessary, to protect the subjects' health and safety or the integrity of the study data.

Reasons for discontinuation include, but are not limited to, the following:

- Adverse event (specify)
- Pregnancy
- Withdrawal by subject (specify)
- Noncompliance or protocol deviation/violation (specify)
- Lost to follow-up (specify)
- Other (specify)

Subjects who discontinue after taking the first dose of study drug will not be replaced. Subjects who discontinue before taking study drug will be replaced.

In the event of a premature study discontinuation, subjects will undergo the procedures for the EOS Visit (or EOE Visit if in the Part D Extension) described in [Section 6.9](#). The reason for discontinuation must be recorded in the case report form (CRF).

4.6. Medication and Activity Restrictions

Subjects must not take any OTC medication (including nutritional or dietary supplements, herbal preparations, or vitamins) \leq 7 days prior to the first dose of study drug until the EOS (or EOE) Visit without evaluation and approval by the Investigator. For subjects with CG or GALK-deficient Galactosemia, use of medications to treat Galactosemia complications will be permitted by approval of the Investigator.

Subjects must not take any prescription medication, except that allowed per protocol in this section, from 14 days prior to the first dose of study drug until the EOS (or EOE) Visit without evaluation and approval by the Investigator. For subjects with CG or GALK-deficient Galactosemia, use of medications to treat Galactosemia complications will be permitted by approval of the Investigator.

In addition, use or consumption of the following are not permitted:

- Tobacco- or nicotine-containing products within 6 months prior to the first dose of study drug (including negative cotinine test at screening) through the EOS Visit (subjects in Parts A, B, and C only)
- Drugs of abuse (amphetamines, barbiturates, benzodiazepines, cocaine, cannabinoids, opiates) from a negative drug test at screening through the EOS (or EOE) Visit

(Exception: Subjects with CG or GALK-deficient Galactosemia may take such drugs or drugs that produce positive drug screening results if clinically indicated and on a stable dose for ≥ 1 month prior to screening and throughout the study. Drugs of abuse are defined by the local regulations where a patient lives [i.e., a positive result for cannabinoids will not be disqualifying if this drug is legal/permitted in the patient's hometown].)

- Treatment with sensitive substrates of BCRP (e.g., rosuvastatin, sulfasalazine) or potent inhibitors of BCRP (e.g., cyclosporine A) within 5 half-lives prior to the first dose of study drug through the last dose of study drug
- Treatment with sensitive substrates of OAT1 and OAT3 (e.g., famotidine, adefovir, furosemide, ganciclovir, cefaclor, ceftizoxime, pen-G) within 5 half-lives prior to the first dose of study drug through the last dose of study drug
- Treatment with sensitive substrates of cytochrome P450 3A4 (CYP3A4) (e.g. midazolam, triazolam, buspirone, alfentanil, dronedarone, eletriptan, conivaptan, lovastatin, simvastatin), or CYP2B6 (e.g. bupropion), or CYP2C19 (e.g. omeprazole), or CYP1A2 (e.g. alosetron, caffeine, duloxetine, melatonin, ramelteon, tasimelteon, tizanidine) within 5 half-lives prior to the first dose of study drug through the last dose of study drug
- Drugs potentially associated with transaminase elevations, such as mirtazapine within 5 half-lives prior to the first dose of study drug through the last dose of study drug.
- Beverages or foods that contain alcohol, high levels of sorbitol, grapefruit, poppy seeds, broccoli, Brussels sprouts, pomegranate, star fruit, char-grilled meat, or caffeine/xanthine from 48 hours prior to the first dose of study drug through the visit before the EOS (or EOE) Visit (allowance for an isolated single incidental consumption may be evaluated and approved by the Investigator based on the potential for interaction with the study drug)
- The following following potentially nephrotoxic drugs within 5 half-lives prior to the first dose of study drug through the last dose of study drug: amitriptyline, aspirin, doxepin, lithium, amphotericin B, foscarnet, ganciclovir, pentamidine, rifampin, antiretrovirals (e.g. adefovir, tenofovir), calcineurin inhibitors (e.g. cyclosporine, tacrolimus), angiotensin-converting enzyme inhibitors, angiotensin receptor blockers, clopidogrel, ticlopidine, pamidronate, zoledronate, statins, chemotherapeutics, contrast dye, loop diuretics, thiazides, triamterene, allopurinol, gold therapy, haloperidol, quinine, ranitidine

If the potential subject is currently taking any of the prohibited medications, a review with the investigator with consultation with the sponsor is encouraged. This is due to variability in potential drug-drug interactions and interpretation of what medications are sensitive substrates or moderate or severe inhibitors or inducers versus AT-007. As such, after investigation an exception to an above prohibited medication may be allowed.

A summary of potential drug-drug interactions (DDI) based on in vitro studies is provided in [Appendix A](#).

Permitted concomitant medications in this study are the following:

- Female hormonal contraceptives or hormone replacement therapy (Parts A, B, C, D, E, and D Extension)
- Concomitant medications and dietary supplements with stable doses maintained for ≥ 1 month prior to screening and through the last dose of study drug (Parts A, B, C, D, E, and D Extension)
- Background medications for the management of subjects with history of seizures (Parts D, E, and D Extension) as long as they are not sensitive substrates of BCRP, OAT1, OAT3, CYP3A4, CYP2B6, CYP2C19, or CYP1A2 or potent inhibitors of BCRP. Patients who switched to an allowed anti-epileptic medication will need to be stable on treatment for at least 30 days prior to the first dose of study drug.

Subjects must not donate blood or plasma from 3 months prior to the first dose of study drug through the EOS (or EOE) Visit. It is recommended that blood/plasma donations not be made for at least 30 days after the EOS (or EOE) Visit.

Subject must not engage in strenuous exercise from 48 hours prior to the first dose of study drug through the EOS (or EOE) Visit.

Subjects must stay in the CRU during the time periods designated in the Schedules of Assessments ([Appendix A](#), [Appendix B](#), [Appendix C](#), [Appendix D](#), [Appendix E](#), and [Appendix F](#)).

4.7. Contraception Requirements

Female subjects must be one of the following:

- Non-childbearing potential
- OR
- Childbearing potential and agree to use an acceptable form of birth control from screening until 30 days after the EOS (or EOE) Visit

Women of non-childbearing potential are defined as follows:

- Surgically sterile (i.e., had a bilateral tubal ligation, hysterectomy, or bilateral oophorectomy ≥ 6 months prior to the first dose of study drug)
- OR
- Postmenopausal for at least 1 year prior to the first dose of study drug.

Subjects claiming postmenopausal status will have an FSH test performed at screening to confirm postmenopausal status.

Females of childbearing potential must agree to use an acceptable form of birth control from the time point specified in the list below (or screening if no time point specified) until 30 days after the EOS (or EOE) Visit. The following are acceptable birth control methods for this study:

- Vasectomized partner (at least 6 months prior to dosing);
- Non-surgical permanent sterilization (e.g., Essure[®] procedure) at least 3 months prior to dosing;
- Double barrier method (e.g., diaphragm plus condom);
- Intrauterine device (IUD);
- Abstinence (and must agree to use a double barrier method if they become sexually active during the study);
- Implanted or intrauterine hormonal contraceptives in use for ≥ 6 consecutive months prior to dosing;
- Oral, patch, or injected contraceptives, or vaginal hormonal device (i.e., NuvaRing[®]) in use for ≥ 3 consecutive months prior to dosing.

Female subjects must agree to provide any requested information about the pregnancy should contraception fail and a pregnancy occurs within 90 days after the last dose of study drug.

A male subject with sexual partners who could become pregnant must meet the following criteria:

- Participant is unable to procreate, defined as surgically sterile (i.e., had a vasectomy ≥ 6 months prior to screening)

OR

- Participant is able to procreate and agrees to use an acceptable contraceptive method from screening until 30 days after the EOS (or EOE) Visit. An acceptable method of contraception includes one of the following:
 - Abstinence from heterosexual intercourse
 - Condom with spermicide or condom with intra-vaginally applied spermicide

Male subjects must agree to provide any requested information about partner pregnancy should contraception fail and a pregnancy occurs within 90 days after the subject's last dose of study drug. If a partner pregnancy occurs, consent from the pregnant partner will also be obtained before any information about the pregnancy is requested or collected.

5. STUDY TREATMENTS

Subjects will be randomly assigned ([Section 5.2](#)) to either AT-007 or matching placebo in Parts A, B, D, E, and D Extension. The number of subjects to be treated with AT-007 and the number of subjects to be treated with placebo in each cohort are described in [Section 3.3](#).

Subjects will be assigned to open-label AT-007 in Part C.

5.1. Study Drug Supplies

AT-007 drug substance is manufactured according to current Good Manufacturing Practice (GMP) by Worldwide Clinical Trials, Early Phase Services, located in San Antonio, TX. The chemical name for AT-007 is 2-(4-oxo-3-((5-(trifluoromethyl)benzo[d]thiazol-2-yl)methyl)-3,4-dihydrothieno[3,4-d]pyridazin-1-yl)acetic acid. Applied Therapeutics Inc. will supply sufficient quantities of the study drug formulation to allow completion of this study.

AT-007 and matching placebo will be shipped to the appropriate study sites pursuant to site standard operating procedures (SOPs). Upon receipt of the study drug products, the supplies will be inventoried and stored in an environmentally controlled and secure, limited access area. The lot numbers of the drugs along with the expiration dates (where available) will be recorded and copies of the Certificate of Analysis (where available) will be maintained on file. Records will be maintained of the receipt and dispensation of the drugs supplied.

Details regarding study drug shiptment, preparation, and dispensation are in a separate pharmacy manual. Dosing will be weight based. AT-007 (or matching placebo) will be taken orally, QD, under fasted conditions. Doses will be rounded according to the available stock keeping unit (SKU) as described in the Pharmacy Manual.

Retention samples of investigational AT-007 will not be required. At the conclusion of the study, any unused study drug will be returned to the Sponsor or destroyed by the study center pursuant to written authorization by the Sponsor and applicable regional/local regulations.

5.2. Study Drug Assignment and Blinding

Up to 116 subjects are planned to be dosed in this study:

- Part A: 5 cohorts of 8 healthy subjects each
- Part B: 2 cohorts of 6 healthy subjects each and 2 cohorts of 8 healthy subjects each
- Part C: 3 cohorts of 4 healthy subjects each
- Part D: 3 cohorts of 6 subjects with CG each
- Part E: 1 to 3 cohorts of 6 subjects with GALK-deficient Galactosemia each
- Part D Extension: 1 to 2 cohorts with a combined total of 28 subjects with CG

Note: The number of cohorts and total number of subjects may increase if doses above 40 mg/kg are tested in additional cohorts (see [Section 1.4](#)). In Parts D and E, the overall number of subjects per cohort may be increased up to 8 subjects to address any potential lost-to-follow-up among subjects treated with either placebo or AT-007. In Parts D and E, subjects treated with study drug (placebo or AT-007) in a cohort may be randomized to treatment in another cohort (separate consent required) within the same Part (assuming no safety or tolerability issues in the prior

cohort) as long as there is a washout period ≥ 5 days between the last dose in a cohort and the first dose in the next cohort. Both de novo and Part D subjects with CG may participate in Part D Extension (separate consent required) (see [Section 3.3.6](#) for details regarding when a Part D subject can start study drug in the Part D Extension).

In Parts A, B, D, E, and D Extension, subjects will be randomized to receive either active drug (AT-007) or placebo (see [Section 3.3](#) for the number of subjects to be randomized to each treatment within each cohort). Each subject will receive an assigned treatment based on the randomization schedule prepared by the study statistician.

Parts A and B will be double-blinded (the Sponsor/CRO, clinical site staff [except for unblinded pharmacist for Parts A and B], and the subjects will not know which subjects are treated with AT-007 or placebo).

In Part C, all subjects will be assigned to receive active drug (AT-007). Part C will be open-label.

In Parts D, E, and D Extension, the clinical site staff (except for the unblinded pharmacist) and the subjects will be blinded to study treatment. The Sponsor/CRO will not be blinded to study treatment because the relationship between exposure in Parts D, E, and D Extension (subjects with galactosemia) vs. exposure in healthy subjects will need to be evaluated on an ongoing basis to ensure that AT-007 blood levels remain within the limits achieved in Part B. This process will minimize the number of subjects with galactosemia potentially exposed to plasma concentrations of AT-007 not previously tested and shown to be safe in healthy subjects.

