Part A of the study started first. Part A Cohort 5 (40 mg/kg single dose) was recently added to the protocol (version 4.0) and results showed the dose was safe and well tolerated. Part B started after all subjects in Cohorts A1 through A4 completed the study (minus the EOS Visit). Given that the results for 40 mg/kg in Cohort A5 were acceptable, Part B Cohort 4 (40 mg/kg) will start with this version of the protocol (version 5.0). The first cohort in Part C (C1) started after both safety and PK data from

Cohorts B1 and B2 were reviewed. Cohort C1 was conducted simultaneously with Cohort B3 and used the same dose as Cohort B2 (10 mg/kg). The second cohort in Part C (C2) started after safety and PK data from Cohort B3 were reviewed and used the same dose as Cohort B3 (20 mg/kg); safety and PK results for Cohort C1 were also considered before starting Cohort C2. The third cohort in Part C (C3) will start with this version of the protocol (version 5.0) and use the same dose as Cohort B4 (given the results from Cohort A5); safety and PK results for Cohort C2 were also considered before starting Cohort C3. The first cohort in Part D (D1) started after all subjects in Cohorts A1 through A4 completed the study including the EOS Visit and all subjects in Cohorts B1 and B2 completed the study (minus the EOS Visit). The dose for Cohort D1 (5 mg/kg) was not higher than the dose for Cohort B2 (10 mg/kg). The second cohort in Part D (D2) started after all subjects in Cohort B3 completed the study (minus the EOS Visit) and the dose level (20 mg/kg) was the same as that for Cohort B3. The third cohort in Part D (D3) will start after all subjects in Cohort B4 complete the study (minus the EOS Visit) and the dose level will not be higher than the 40 mg/kg dose used for Cohort B4. The starting dose for Part E (Cohort E1) will be the most clinically appropriate dose as determined by the evaluation of available safety, tolerability, and PD (reduction in galactitol level) in Part D and the dose will not be higher than the highest acceptable dose in Part D at the time of starting Part E (after all subjects complete Cohorts D1 and D2 but may be before, during, or after Cohort D3). The Safety Review Committee (SRC) reviewed/will review safety data before each dose escalation and before the start of Parts B, C, D, and E. Also, the Sponsor reviewed/will review all PK and galactitol data as they become available.

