n = number of subjects; MAD = multiple ascending dose; QD = once daily; SAD = single ascending dose; TBD = to be determined.

Note: The number of cohorts and total number of subjects may increase if doses above 40 mg/kg are tested in additional cohorts (see [Section 1.4](#)). The overall number of subjects per cohort may be increased up to 8 subjects to address any potential lost-to-follow-up among subjects treated with either placebo or AT-007. Subjects treated with study drug (placebo or AT-007) in a cohort may be randomized to treatment in another cohort (separate consent required) within the same Part (assuming no safety or tolerability issues in the prior cohort) as long as there is a washout period \geq 5 days between the last dose in a cohort and the first dose in the next cohort. This table has been updated to reflect the dose levels actually tested in completed Cohorts D1 and D2. The dose level for Cohort D3 is TBD as of the writing of protocol version 5.0.

3.3.5. Part E: Single Ascending Dose (SAD) and Multiple Ascending Dose (MAD) in Subjects with GALK-deficient Galactosemia

The starting dose level for subjects with GALK-deficient Galactosemia will be the most clinically appropriate dose as determined by the evaluation of safety, tolerability, and PD (reduction in galactitol level) in Part D cohorts completed at the time of starting Part E ([Table 6](#)). If needed, additional dose levels may be tested in additional cohorts. If applicable, dose levels for subsequent cohorts in Part E will be based on safety data through Day 12 and at least single dose PK and galactitol results from the previous cohort(s) in Part E and possibly additional cohorts in Part D.

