9.2. Statistical Methods

Detailed statistical methods will be provided in a Statistical Analysis Plan (SAP) that will be finalized before database lock.

NOTE: Part E and Part D Extension results might not be included in the CSR. If the Part E and/or Part D Extension results are not included in the CSR, they will be summarized and presented in a separate report or CSR addendum.

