| Chief Medical Officer, Applied Therapeutics Inc. | |

REVISION HISTORY

| Version | Date | Author | Comments |
|------------|------------|----------------|---|
| Final V1.0 | 03DEC2019 | [name] | Initial document |
| Final V2.0 | 14JULY2020 | [name] | Added Part D Extension and E. |
| Final V3.0 | 20JUL2021 | [name] | Addressed client comments on 25May2021: Updated Enzyme activity categories. Added forest plot for Subgorup analysis of blood Galactitol. Update Biomarker section 7.11 and LOT for biomarker related tables. |

LIST OF ABBREVIATIONS AND DEFINITIONS OF TERMS

| Abbreviation or Specialist Term | Explanation |
|------------------------------------|---|
| AE | adverse event |
| Ae_{t1-t2} | amount of unchanged drug excreted though urine |
| ALT | alanine transaminase |
| ALP | alkaline phosphatase |
| ALT | alanine transaminase |
| AST | aspartate transaminase |
| AUC | area under the concentration-time curve |
| $\mathrm{AUC}_{\mathrm{inf}}$ | Area under the concentration time curve from time zero extrapolated to infinity |
| AUC _{last} | Area under the concentration time curve from time zero to the time of the last quantifiable concentration; calculated using the linear trapezoidal rule |
| AUC _{tau} | area under the concentration-time curve within the dosing interval |
| AUC _{Extrap} (%) | percentage of AUCinf based on extrapolation |
| BLQ | below the quantifiable limit |
| BUN | blood urea nitrogen |
| CI | confidence interval |
| CL/F | Clearance after extravascular administration |
| CG | classic galactosemia |
| C _{last} | last quantifiable concentration determined directly from individual concentration time data |
| C_{max} | maximum concentration, determined directly from individual concentration time data |
| CL_R | renal clearance |
| CRA | clinical research associate |
| CRU | clinical research unit |
| CSF | cerebrospinal fluid |
| CSR | clinical study report |
| | |

| Abbreviation or Specialist Term | Explanation |
|------------------------------------|---|
| C_{trough} | trough or predose concentration |
| CV | coefficient of variation |
| DLT | dose limiting toxicity |
| DMP | Data Management Plan |
| ECG | Electrocardiogram |
| eCRF | electronic case report form(s) |
| EOE | end of extension |
| EOS | end-of-study |
| fe_{t1-t2} | fraction of the administered dose excreted in urine over the interval from time t1 to time t2 |
| FSH | follicle-stimulating hormone |

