3.1.3 Randomization and Treatment Assignments

Subjects will be randomly assigned to either AT-007 or matching placebo in Parts A, B, D, E and D Extension. The number of subjects to be treated with AT-007 and the number of subjects to be treated with placebo in each cohort are described in Section 3.1.4. Subjects will be assigned to open-label AT-007 in Part C.

Up to 116 subjects are planned to be dosed in this study:

- Part A: 5 cohorts of 8 healthy subjects each
- Part B: 2 cohorts of 6 healthy subjects each and 2 cohorts of 8 healthy subjects each
- Part C: 3 cohorts of 4 healthy subjects each
- Part D: 3 cohorts of 6 subjects with CG each
- Part E: 1 to 3 cohorts of 6 subjects with GALK-deficient Galactosemia each
- Part D Extension: 1 to 2 cohorts with a combined total of 16 subjects with CG

The number of cohorts and total number of subjects may increase if doses above 40 mg/kg are tested in additional cohorts.

In Parts A, B, D, E and D Extension, subjects will be randomized to receive either active drug (AT-007) or placebo. Each subject will receive an assigned treatment based on the randomization schedule prepared by the study statistician.

Parts A and B will be double-blinded (the Sponsor/ CRO, clinical site staff [except for unblinded pharmacist for Parts A and B], and the subjects will not know which subjects are treated with AT-007 or placebo).

In Part C, all subjects will be assigned to receive active drug (AT-007). Part C will be open-label.

In Parts D, E and D Extension the clinical site staff [except for the unblinded pharmacist], and the subjects will be blinded to study treatment. The Sponsor/CRO will not be blinded to study treatment in Part D, as the relationship between exposure in Parts D, E and D Extension (subject with galactosemia) vs. exposure in healthy subjects will need to be evaluated on an ongoing basis to ensure that AT007 blood level remain within the limits achieved in Part B. This process will minimize the number of subjects with galactosemia potentially exposed to plasma concentrations of AT-007 not previously tested and shown to be safe in healthy subjects.

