7.4 Examination of Subgroups

For Parts D, E and D Extension, blood galactitol changes will be analyzed based on below subgroup categories if data permit:

- Gender: Male / Female
- Age: $\langle 21 \text{ years} / \rangle = 21 \text{ years and } \langle 30 \text{ years} / \rangle = 30 \text{ years}$
- BMI: $<22 \text{ kg/m}^2 / 22-25 \text{ kg/m}^2 / >25 \text{ kg/m}^2$
- Enzyme activity: <0.1%, 0.1-0.4%, >0.4%

Additionally forest plot will be displayed for Part D and E at Day 32 and for Part D extension at Day 90/EOT for blood galactitol results.

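### SAP V3.0 revised the Part D galactitol analyses after D1 and D2 were complete and their unblinded data were open to the Sponsor; say so, and lead with by-arm change at fixed times

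*Protocol*

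**What the plan says.** **Blinding and data access.** Protocol Section 5.2 blinds site staff and subjects in Parts D, E and D Extension, but "The Sponsor/CRO will not be blinded to study treatment", because exposure in these parts has to be compared with exposure in healthy subjects as the study runs. SAP Section 3.1.3 agrees: "The Sponsor/CRO will not be blinded to study treatment in Part D". The Synopsis adds that "the Sponsor reviewed/will review all PK and galactitol data as they become available". Protocol Section 3.4 has the Sponsor review D1 and D2 single-dose galactitol before the D3 dose is confirmed.

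**Timing rule.** Protocol Section 9.2: "Detailed statistical methods will be provided in a Statistical Analysis Plan (SAP) that will be finalized before database lock". SAP Section 4 places the lock after Part D completes and gives no date.

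**State of Part D.** The note to Protocol Table 5, which describes the position at protocol version 5.0, says "This table has been updated to reflect the dose levels actually tested in completed Cohorts D1 and D2".

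**The revision.** The SAP revision history for V3.0 (20 July 2021) reads "Addressed client comments on 25May2021: Updated Enzyme activity categories". The same entry records a new forest plot for the blood galactitol subgroups and an update of Section 7.11 and its tables. The categories are now "Enzyme activity: <0.1%, 0.1-0.4%, >0.4" percent (SAP 7.4, repeated in 7.11).

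**The galactitol measure.** SAP 7.11 takes the lowest plasma value on Day 1, 12 or 32 and compares it with the mean of two predose values (Day -1 and time 0 on Day 1). Protocol 9.2.9 promises only descriptive statistics and leaves the detail to the SAP.

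**The concern.** Finalizing a plan before lock protects analysis choices only if those who ask for changes cannot yet see results by treatment. In Part D the Sponsor can, by design. A change to a galactitol definition or a subgroup boundary, made at client request after two of the three cohorts had finished, could therefore have been made with treatment-level results in view. I read the client as the Sponsor.

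A reader of the study report would not easily see this. SAP Sections 7.4 and 7.11 present the analyses without qualification, and Section 1 calls the SAP consistent with the protocol's statistical section. At stake is how much weight to give two statements: how far AT-007 lowers galactitol, and which enzyme-activity group responds.

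The form of the main measure raises the stakes. A lowest-of-many value shows a fall in anyone whose galactitol fluctuates, treated or not.

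**Working it through.** **1. Dates.** Protocol version 6.0 is dated 05 May 2020 (SAP Section 1). Version 5.0 must be earlier, so D1 and D2 were complete before that date.
- 05 May 2020 to the client comments of 25 May 2021: 385 days.
- 05 May 2020 to SAP V3.0 on 20 July 2021: 441 days.
- SAP V2.0 (14 July 2020) to V3.0: 371 days.

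D1 and D2 hold 2 × 6 = 12 of the 18 planned Part D subjects: 2 × 4 = 8 on AT-007 and 2 × 2 = 4 on placebo.

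**2. What is disclosed.**
- The revision history gives the date, the source and the topics of the V3.0 changes.
- SAP Section 4 lists Part D galactitol subgroup analyses as additional to the protocol.
- Section 4 does not mention the lowest-value measure, the two-sample baseline (SAP 7.1 and Protocol 9.2.1 use the predose value on Day 1 or Day -1) or the revised cut-points. It does not say that unblinded D1/D2 data were available when V3.0 was written.

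**3. Size of the enzyme subgroups.** Three categories across three doses plus pooled placebo make 3 × 4 = 12 cells. With 18 subjects that is 18/12 = 1.5 per cell, and 4/3 ≈ 1.3 AT-007 subjects per category per dose. Moving a boundary past one subject can change the picture.

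**4. The lowest-value rule with no drug effect.** The documents give no variability for galactitol, so this is an illustration over a range.
- Samples (Protocol Appendix D; biomarker times match PK times): 11 after the Day 1 dose, 10 for Day 12 (predose to 24 h) and 12 for Day 32 (predose to 48 h). 11 + 10 + 12 = 33.
- Model: each value is 1 + CV × e, with e standard normal, serial correlation 0 to 0.8 and no trend. Baseline is the mean of two values.
- Measure: (lowest of 33 − baseline)/baseline, averaged over simulated subjects.

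| Assumed within-subject CV | Average apparent fall (correlation 0.8 to 0) |
|---|---|
| 5% | 8.3% to 10.3% |
| 10% | 16.3% to 20.4% |
| 15% | 24.2% to 30.4% |
| 20% | 32.0% to 40.4% |

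Hand check at CV 10%, no correlation: the expected minimum of 33 standard normals is about −2.08, so the lowest value averages 1 − 0.208 = 0.792. The mean of 1/baseline is about 1 + 0.10²/2 = 1.005. Then 0.792 × 1.005 − 1 ≈ −0.204, a fall of 20.4%.

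Two variations change little at CV 10%. Confining the correlation to samples around the same dosing day gives about 17% to 20%. Counting only samples taken on Days 1, 12 and 32 themselves (8 + 9 + 9 = 26) gives about 15% to 19%.

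For comparison, one fixed scheduled time under the same model gives 1.005 − 1 = +0.5% with no correlation and stays below 1% in size up to correlation 0.8. The artefact comes from taking the minimum.

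**The case against.** A reader might infer that the Part D galactitol results are post hoc, chosen from the data and passed off as planned. The documents do not support that.
- The texts of V1.0 and V2.0 are not available. The revision history says the enzyme categories were updated, which implies that categories already existed; only the forest plot is described as added. The lowest-value measure may date from V1.0.
- The changes are not hidden. They are dated and attributed in the revision history, Section 4 lists the subgroup analyses, and these are conditional on the data permitting.
- Sponsor unblinding has a stated reason, exposure monitoring, and galactitol also guides escalation in Part D (Protocol 3.5). Nothing shows that galactitol was reviewed by enzyme group, or that D3 results were in hand when V3.0 was written.

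A reader might also infer an inflated false-positive rate. The plan specifies no galactitol test or alpha, biomarkers are summarized descriptively, and Protocol 9.2.10 marks efficacy analyses as not applicable. There is no nominal error rate to inflate.

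It is also fair to say that placebo subjects would show the same lowest-value artefact, so a comparison with placebo largely cancels it.

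All of this stands, and it limits the point. It does not answer the gap in Section 4, nor the use of a measure that shows a fall without a drug effect.

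**Conclusion.** The point holds in a limited form. V3.0 revised the enzyme cut-points, added the forest plot and updated Section 7.11 at least 441 days after D1 and D2 were complete, with their unblinded galactitol open to the Sponsor. Pre-lock finalization therefore gives these choices no protection. Whether the data influenced them is unknown.

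The risk is selective presentation of a secondary, descriptive endpoint. The primary safety objective is untouched. The sized part is the lowest-value measure: an apparent average fall of about 16–20% with no drug effect at a CV of 10%, and about 8–40% across CVs of 5–20%. That rests on assumed variability, normal errors and no time trend. The timing rests on version 5.0 preceding version 6.0. The change should be made; it does not call the design into question.

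**What to change.** 1. **SAP 7.11, main result.** Make the main Part D galactitol result a summary by arm (each AT-007 dose and pooled placebo) of observed values and change from baseline at fixed scheduled times. Keep the lowest-value maximum reduction as supportive, always beside placebo. This is my recommendation; Protocol 9.2.9 does not require it. The galactitol-over-time figures in SAP Section 8 are listed on the PK population, which requires an AT-007 dose (SAP 7.5), so they should move to the Safety population for placebo to appear.
2. **SAP Section 4.** List each definition changed in V3.0 and state that unblinded D1/D2 data were available to the Sponsor at the time. For Part D, label as post hoc/exploratory the revised enzyme subgroups, the forest plot and any 7.11 measure that V1.0 or V2.0 does not show.
3. **Part E and D Extension.** Fix definitions and cut-points before biomarker results from those parts are released, where this is still possible. Section 7.11 covers only Parts D and E, so the Extension has no galactitol measure there, although 7.4 plans an Extension forest plot.

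The cost is SAP wording, table titles and table order, with no change to design, dosing or data collection. The downside is a slightly less favourable Part D galactitol claim.
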